## 2 ETHICS AND REGULATORY OBLIGATIONS

### 2.1 Institutional Review Board (IRB)

Written IRB approval of this protocol must be obtained before the study is initiated. Compliance with Title 21 of the US Code of Federal Regulations (CFR), Part 56, is required in order to protect the rights and welfare of human subjects involved in this study.

### 2.2 Ethical Conduct of the Study

The study will be conducted in accordance with the ethical principles that have their origins in the Declaration of Helsinki and its amendments. In addition, the study will be performed in compliance with Good Clinical Practices (GCP), including the archiving of essential documents.

### 2.3 Subject Information and Consent

The Informed Consent Form will be reviewed and approved by the IRB. The purpose, duration and possible risks and benefits will be explained to each potential subject. Consent in writing must be obtained from the subject before enrollment into the study. Consents will be signed and dated as required by Title 21 of CFR, Part 50. The consent will also comply with the requirements of the Health Insurance Portability and Accountability Act (HIPAA). The original, signed Informed Consent Form will be retained by the Investigator. A signed copy of the Informed Consent Form will be given to the subject. Each subject will be assigned a subject number that will be used in lieu of the subject's name on further research documentation.

## 3 INTRODUCTION

### 3.1 Overview of Psoriasis

Psoriasis is a chronic immunological disease characterized by infiltration of the skin with activated T cells and by abnormal keratinocyte proliferation and differentiation, resulting in marked inflammation and thickening of the epidermis. Psoriasis affects 1-3% of the world population, making it one of the most prevalent inflammatory immunological diseases. There are several clinical subtypes of psoriasis: plaque, guttate, erythrodermic, inverse, and pustular. Plaque psoriasis is the most common type of

psoriasis affecting 75-80% of psoriasis sufferers. It presents as raised silvery scale, which can cover large areas, with underlying erythema, itching, and discomfort.

### **3.2 Rationale for Treating Plaque Psoriasis with OTEZLA® + Enstilar®**

OTEZLA® and Enstilar® are both effective in treating psoriasis. The pivotal OTEZLA® Phase III trials (ESTEEM) determined that apremilast was effective in treating moderate to severe plaque psoriasis. The primary endpoint at week 16 demonstrated significantly more apremilast-treated patients (33.1%) achieved the primary end point (PASI-75 at week 16) than did placebo patients (5.3%). Combination regimens that utilize a systemic agent with light therapy and/or a topical agent are becoming the standard of care in the United States and Europe, confirming the observation of Lebwohl et al in 2004, that the use of two or more therapies to treat patients with moderate to severe psoriasis seems to be the rule rather than the exception. Topical steroids play an important role in the long term management of psoriasis and data from the COBRA trial suggests that super potent topical corticosteroids are appropriate and well tolerated for use when added to existing therapeutic regimens i.e. phototherapy, systemic and biologic therapy. A post hoc analysis of the Phase 3 ESTEEM 1 trial of apremilast was conducted to assess the efficacy and safety of apremilast with and without topical therapies and/or UVB phototherapy. The analysis focused on the sub-group of patients who did not achieve PASI 75 at week 32. At week 52, more patients receiving topical therapy and/or phototherapy achieved PASI 75 than did patients with apremilast alone. This study is being conducted to determine if adding topical Enstilar® to Otezla® therapy can help patients who received a partial response at week 8 reach PASI 75 by week 12.

## **4. STUDY OBJECTIVE**

To explore the effectiveness and safety of combining OTEZLA® and Enstilar® and to determine if add-on Enstilar® therapy can help partial responders at week 8 achieve PASI 75 at week 12.

## **5. INVESTIGATIONAL PLAN**

### **5.1 Overall Study Design and Plan**

50 subjects affected with plaque psoriasis with body surface area greater than or equal to 10%, and physician's global assessment greater than or equal to 3 and PASI greater than or equal to 12 will receive OTEZLA® 30 mg twice daily for 8 weeks.

Patients who do not achieve at least a PASI 25 at week 8 will be discontinued from treatment and study procedures.

At week 8, subjects who have achieved a PASI 25-74 will receive Enstilar® (calcipotriene and betamethasone dipropionate) Foam, 0.005%/0.064% once daily for 4 weeks in addition to continuing OTEZLA® BID. These patients will then discontinue Enstilar® at week 12 and remain on OTEZLA® monotherapy through week 16.

Patients who achieve PASI 75 at week 8 will remain enrolled in the study and continue OTEZLA® 30mg BID through week 16. These subjects will not receive Enstilar® add-on therapy.

## **5.2 Study Population Criteria**

Males and females ≥ 18 years of age with moderate-to-severe chronic plaque psoriasis

### **5.2.1 Inclusion Criteria**

Patients who meet all of the following criteria will be enrolled in the study:

1. Male or female adult ≥ 18 years of age
2. Diagnosis of chronic plaque-type psoriasis
3. Moderate to severe plaque type psoriasis as defined at baseline by:
  - Physician's Global Assessment (PGA) score of 3 or greater
  - Body Surface Area (BSA) affected by plaque-type psoriasis of 10% or greater
  - Psoriasis Area Severity Index of 12 or greater
4. Able and willing to give written informed consent prior to performance of any study-related procedures
5. Must be in general good health (except for disease under study) as judged by the Investigator, based on medical history, physical examination, clinical laboratories, and urinalysis. (NOTE: The definition of good health means a subject does not have uncontrolled significant co-morbid conditions).
6. Females of childbearing potential (FCBP)† must have a negative pregnancy test at Screening and Baseline. While on investigational product and for at least 28 days after taking the last dose of investigational product, FCBP who engage in activity in which conception is possible must use one of the approved contraceptive§ options described below:

Option 1: Any one of the following highly effective methods: hormonal contraception (oral, injection, implant, transdermal patch, vaginal ring); intrauterine device (IUD); tubal ligation; or partner's vasectomy;

**OR**

Option 2: Male or female condom (latex condom or nonlatex condom NOT made out of natural [animal] membrane [for example, polyurethane]; PLUS one

additional barrier method: (a) diaphragm with spermicide; (b) cervical cap with spermicide; or (c) contraceptive sponge with spermicide.

† A female of childbearing potential is a sexually mature female who 1) has not undergone a hysterectomy (the surgical removal of the uterus) or bilateral oophorectomy (the surgical removal of both ovaries) or 2) has not been postmenopausal for at least 24 consecutive months (that is, has had menses at any time during the preceding 24 consecutive months). The female subject's chosen form of contraception must be effective by the time the female subject is randomized into the study (for example, hormonal contraception should be initiated at least 28 days before randomization).

### 5.2.2 Exclusion Criteria

Patients will NOT be enrolled in this study if they meet any of the following criteria:

1. Other than psoriasis, any clinically significant (as determined by the Investigator) cardiac, endocrinologic, pulmonary, neurologic, psychiatric, hepatic, renal, hematologic, immunologic disease, or other major disease that is currently uncontrolled.
2. Prior history of suicide attempt at any time in the subject's life time prior to screening or randomization, or major psychiatric illness requiring hospitalization within the last 3 years.
3. Pregnant or breast feeding, or considering becoming pregnant during the study.
4. Active substance abuse or a history of substance abuse within 6 months prior to Screening.
5. Malignancy or history of malignancy, except for:
  - a. treated [ie, cured] basal cell or squamous cell carcinomas;
  - b. treated [ie, cured] cervical intraepithelial neoplasia (CIN) or carcinoma in situ of cervix with no evidence of recurrence within the previous 5 years.
6. Use of any investigational drug within 4 weeks prior to randomization, or within 5 pharmacokinetic/pharmacodynamic half lives, if known (whichever is longer).
7. Prior treatment with apremilast.
8. Forms of psoriasis other than chronic plaque-type (e.g., Pustular erythrodermic and/or guttate psoriasis) or drug induced psoriasis
9. Subject has previously used any biologic agent for psoriasis.

10. Use of oral systemic medications for the treatment of psoriasis within 4 weeks (includes, but not limited to, oral corticosteroids, methotrexate, acitretin and cyclosporine).
11. Patient used topical therapies to treat psoriasis on the hands and/or feet within 2 weeks of the Baseline Visit (includes, but not limited to, topical corticosteroids, vitamin D analogs, or retinoids).
12. Patient received UVB phototherapy within 2 weeks of Baseline.
13. Patient has a known hypersensitivity to the excipients of OTEZLA® or Enstilar® as stated in the label.
14. Any condition which would place the subject at unacceptable risk if he/she were to participate in the study.

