### **5.6 Study Procedures and Assessments**

This protocol will consist of a Screening Period (0-30 days), followed by an open-label treatment period of OTEZLA® for 8 weeks (Period A). At week 8 (Part B), subjects PASI scores will be evaluated and patients who achieve PASI 25-74 will be given add-on Enstilar® treatment for 4 weeks (through week 12) followed by OTEZLA® monotherapy through week 16.

Subjects who do not achieve PASI 25 at week 8 will be discontinued from the study and follow standard of care from their provider.

Subjects who achieve PASI 75 at week 8 will remain on OTEZLA® monotherapy and will not initiate treatment with Enstilar®.

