#### **5.6.2 Inclusion and Exclusion Criteria**

Subjects' eligibility to participate in the study will be determined according to the Inclusion and Exclusion Criteria during the screening period (0 – 30 days prior to the first dose of the study drug). Subjects who ultimately do not satisfy the eligibility criteria except changing treatments and undergoing a washout period, will not be enrolled into the study. Subjects who need to meet eligibility requirements will be asked to make the necessary changes. Subjects who agree and comply will be re-evaluated prior to Baseline.

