### **5.6.7 Psoriasis Area Severity Index (PASI)**

PASI will be determined for all subjects throughout the study. Four anatomical sites (head, trunk, upper and lower limbs) are assessed for erythema, thickness, and scaling on a scale of 0-4 and degree of skin surface area on a scale of 6. The PASI is a validated instrument that has become standard in clinical trials for psoriasis. The sum of the scores are then totaled for the PASI score. Psoriasis Area Severity Index scores range from 0 to 72, with higher scores reflecting greater disease severity. *[See Appendix D](#)*

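### The pre-baseline topical washout covers only hands and feet, so active topicals used elsewhere can lower the baseline PASI

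*Combined protocol and SAP*

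**What the plan says.** Section 5.2.2, item 11, and item 5 of the synopsis exclusions carry the same rule: "Patient used topical therapies to treat psoriasis on the hands and/or feet within 2 weeks of the Baseline Visit". The classes named as examples include topical corticosteroids and vitamin D analogs.

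The neighbouring washouts have no body-site limit. Item 10 reads "Use of oral systemic medications for the treatment of psoriasis within 4 weeks" and item 12 reads "Patient received UVB phototherapy within 2 weeks of Baseline".

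The population is not a hand-and-foot population. Section 5.1 describes "50 subjects affected with plaque psoriasis with body surface area greater than or equal to 10" percent, together with PGA of at least 3 and PASI of at least 12. On PASI, section 5.6.7 says "Four anatomical sites (head, trunk, upper and lower limbs) are assessed for erythema, thickness, and scaling", and Appendix D has the signs scored as they appear on the examination day.

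Baseline PASI then governs what happens to each subject. Section 5.6 says "Subjects who do not achieve PASI 25 at week 8 will be discontinued from the study". Those with a PASI 25-74 response receive Enstilar, and those at PASI 75 stay on OTEZLA alone. The primary endpoint is PASI 75 at week 12 in the add-on group.

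**The concern.** A subject can treat trunk, scalp or limb plaques with an active topical until the day of Baseline and still satisfy every eligibility criterion. Any residual effect enters the baseline score, because PASI is read as seen that day. If the effect then wears off, the subject is measured against a reference that is too low and must improve more in truth to be scored PASI 25 or PASI 75.

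Two things are at stake. A true partial responder near the PASI 25 cut can be discontinued at week 8. That subject never receives Enstilar and falls into neither cohort that section 8.2 summarises. The PASI 75 threshold also becomes stricter for the affected subjects who remain.

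The classes named in item 11 include those of Enstilar's two components (section 5.5.2.1). The baseline can therefore already contain the kind of topical effect the add-on phase is meant to show.

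**Working it through.** **Is the gap closed elsewhere?**

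- Section 5.6.2 foresees treatment changes and washout, and says "Subjects who agree and comply will be re-evaluated prior to Baseline". This helps candidates meet the listed criteria; no listed criterion requires a topical washout away from hands and feet.
- The screening period in section 5.6 runs from 0 to 30 days. It can be zero, so it guarantees no washout.
- Section 5.5.3 permits steroid-free emollients on study. It sets no interval before Baseline.
- Section 5.6.10, item 5, concerns a subject who starts an unapproved therapy. It does not exclude someone for use before Baseline.

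No other text sets a pre-baseline topical rule, so the gap stands.

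**How far could the cuts move?** The plan gives no figure on this point, so there is none to reproduce. From the documents: the PASI 25 and PASI 75 cuts and the PASI 12 entry floor. Assumed, because the documents do not give them:

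- topicals lower whole-body baseline PASI by a fraction s, shown from 5% to 30%;
- the topical stops at Baseline;
- its effect is gone by week 8.

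Let U be the untreated PASI and t the true improvement from U. Baseline is U(1 − s) and the later PASI is U(1 − t), so

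scored improvement = 1 − (1 − t)/(1 − s).

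Setting this equal to a cut c gives the true improvement needed: t = 1 − (1 − c)(1 − s) = c + (1 − c)s.

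- PASI 25: t = 0.25 + 0.75s, a shift of 0.75s.
- PASI 75: t = 0.75 + 0.25s, a shift of 0.25s.
- Entry floor: U(1 − s) ≥ 12, so U ≥ 12/(1 − s).

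| s | True improvement needed for PASI 25 | Shift (points) | True improvement needed for PASI 75 | Shift (points) | Smallest untreated PASI that still enters |
|---|---|---|---|---|---|
| 5% | 28.75% | 3.75 | 76.25% | 1.25 | 12.6 |
| 10% | 32.5% | 7.5 | 77.5% | 2.5 | 13.3 |
| 20% | 40% | 15 | 80% | 5 | 15.0 |
| 30% | 47.5% | 22.5 | 82.5% | 7.5 | 17.1 |

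The shift at the PASI 25 cut is 0.75s/0.25s = 3 times that at the PASI 75 cut.

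**Examples with untreated PASI 20:**

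- s = 5%: baseline 19. A week-8 PASI of 14.5 is a true improvement of 1 − 14.5/20 = 27.5%, scored as 1 − 14.5/19 = 23.7%. The subject is discontinued.
- s = 20%: baseline 16. A week-8 PASI of 13 is 1 − 13/20 = 35% true, scored as 1 − 13/16 = 18.75%. The subject is discontinued.
- s = 20%, upper cut: a PASI of 5 is 75% true, scored as 1 − 5/16 = 68.75%. At week 8 this subject enters the add-on group instead of staying on monotherapy.

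**If the topical continues unchanged.** With the same proportional effect at week 8, the later PASI is U(1 − t)(1 − s), and scored improvement is 1 − (1 − t)(1 − s)/(1 − s) = t. The shift is zero.

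**The case against.** The strongest objection is that the harm needs the topical to stop and its effect to fade. The protocol does not expressly ban non-emollient topicals after Baseline, and someone already using one does not plainly start it. If use simply continues, the shift can be zero. This is right, and it makes the table one branch of the possibilities. It does not remove the gap: stopping at Baseline is equally compatible with the text, and continued use would leave a non-study topical acting during a trial of a topical add-on.

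Second, no effect on the primary result is demonstrated. The flows oppose each other: some true partial responders are lost at the lower cut, while some true PASI 75 responders move into the add-on group at the upper cut. For any one subject a lowered baseline makes PASI 75 harder to reach, which is conservative. This stands, and no net direction is claimed.

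Third, the larger values of s are not supported by anything in the documents. Enrolled subjects must still show PASI 12, BSA 10% and PGA 3 at Baseline. These floors limit the problem without excluding it: at s = 20%, anyone with an untreated PASI of 15 or more still passes the PASI floor.

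Fourth, section 5.6.3 records current anti-psoriasis treatments and section 8.3 records concomitant medications at every visit, so affected subjects can be identified. That allows them to be described separately. It does not recover the unsuppressed baseline or bring back a subject discontinued at week 8.

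Finally, this is a pilot with no hypothesis test, which lowers the stakes. The descriptive proportion is nevertheless the study's main result, and the reference it is measured from should be clean.

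**Conclusion.** The concern holds. As written, the two-week topical exclusion leaves most of the PASI-scored body uncovered, and nothing else in the protocol fills the gap. Under the stop-and-fade assumptions, the true improvement needed rises by 3.75 to 22.5 points at the PASI 25 cut and by 1.25 to 7.5 points at the PASI 75 cut, for assumed suppression of 5% to 30%. If the topical continues with the same proportional effect, neither cut moves.

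These figures show what the rule permits; they do not estimate what will happen. The number of subjects affected and the net bias in the week-12 proportion cannot be derived from the documents. Given the entry floors and the pilot status, this should be corrected, but it does not invalidate the design.

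**What to change.** Delete the five words that confine the exclusion to the hands and feet, in section 5.2.2 item 11 and in synopsis exclusion 5, so that the two-week restriction covers all body areas. Since subjects would then arrive at Baseline off active topicals, any later use would also clearly count as a therapy begun on study under section 5.6.10, item 5.

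The cost is small. Some candidates will need a two-week washout, which takes 14 of up to 30 screening days, and section 5.6.2 already provides for washout and re-evaluation.

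An optional clarification in section 5.5.3 would state that, apart from steroid-free emollients and assigned Enstilar, no topical psoriasis therapy is used from Baseline through week 16. Its cost is that the face, underarms and groin, where Appendix B says Enstilar is not applied, would expressly receive emollients only.

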### **5.3 Source of Subjects and Recruitment Methods**

The Investigator will manage the recruitment of subjects upon approval of the study by the Institutional Review Board. Subjects may be recruited from internal patient lists and outside IRB approved advertisements.

### **5.4 Subject Enrollment and Treatment Assignment**

50 subjects of either gender with moderate-to severe plaque psoriasis will randomized to receive OTEZLA® 30mg BID for 8 weeks. Participation beyond week 8 will be determinate of subject response according to the study design.

## **5.5 STUDY TREATMENT**

### **5.5.1 Apremilast Treatment (OTEZLA®)**

#### **5.5.1.1 Apremilast (OTEZLA®) Description**

OTEZLA® is manufactured by Celgene Corporation. The active ingredient in OTEZLA® tablets is apremilast. Apremilast is a small-molecule inhibitor of phosphodiesterase 4 (PDE4) specific for cyclic adenosine monophosphate (cAMP). The chemical name of apremilast is acetamide, N-[2-[(1S)-1-(3-ethoxy-4-methoxyphenyl)-2-(methylsulfonyl)ethyl]-2,3-dihydro-1,3-dioxo-1H-isoindol-4-yl]. PDE4 inhibition results in increased intracellular cAMP levels. The specific mechanism(s) by which apremilast exerts its therapeutic action in psoriasis patients is not well defined.

### **5.5.1.2 OTEZLA® Warnings and Precautions**

#### **Diarrhea, Nausea, and Vomiting**

There have been postmarketing reports of severe diarrhea, nausea, and vomiting associated with the use of OTEZLA. Most events occurred within the first few weeks of treatment. In some cases patients were hospitalized. Patients 65 years of age or older and patients taking medications that can lead to volume depletion or hypotension may be at a higher risk of complications from severe diarrhea, nausea, or vomiting. Monitor patients who are more susceptible to complications of diarrhea or vomiting. Patients who reduced dosage or discontinued OTEZLA generally improved quickly. Consider OTEZLA dose reduction or suspension if patients develop severe diarrhea, nausea, or vomiting.

#### **Depression**

Treatment with OTEZLA is associated with an increase in adverse reactions of depression. Before using OTEZLA in patients with a history of depression and/or suicidal thoughts or behavior prescribers should carefully weigh the risks and benefits of treatment with OTEZLA in such patients. Patients, their caregivers, and families should be advised of the need to be alert for the emergence or worsening of depression, suicidal thoughts or other mood changes, and if such changes occur to contact their healthcare provider. Prescribers should carefully evaluate the risks and benefits of continuing treatment with OTEZLA if such events occur.

#### **Psoriatic arthritis**

During the 0 to 16 week placebo-controlled period of the 3 controlled clinical trials, 1.0% (10/998) of subjects treated with OTEZLA reported depression or depressed mood compared to 0.8% (4/495) treated with placebo. During the clinical trials, 0.3% (4/1441) of subjects treated with OTEZLA discontinued treatment due to depression or depressed mood compared with none in placebo treated subjects (0/495). Depression was reported as serious in 0.2% (3/1441) of subjects exposed to OTEZLA, compared to none in placebo-treated subjects (0/495). Instances of suicidal ideation and behavior have been observed in 0.2% (3/1441) of subjects while receiving

OTEZLA, compared to none in placebo treated subjects (0/495). In the clinical trials, 2 subjects who received placebo committed suicide compared to none in OTEZLA-treated subjects.

### **Psoriasis**

During the 0 to 16 week placebo-controlled period of the 3 controlled clinical trials, 1.3% (12/920) of subjects treated with OTEZLA reported depression compared to 0.4% (2/506) treated with placebo. During the clinical trials, 0.1% (1/1308) of subjects treated with OTEZLA discontinued treatment due to depression compared with none in placebo-treated subjects (0/506). Depression was reported as serious in 0.1% (1/1308) of subjects exposed to OTEZLA, compared to none in placebo-treated subjects (0/506). Instances of suicidal behavior have been observed in 0.1% (1/1308) of subjects while receiving OTEZLA, compared to 0.2% (1/506) in placebo-treated subjects. In the clinical trials, one subject treated with OTEZLA attempted suicide while one who received placebo committed suicide.

